A Randomized Controlled Trial of Dexamethasone for Dyspnea in Cancer Patients

Principal investigator: [name]

Co-investigators: [name], [name], [name], [name]

Biostatistics Collaborators: [name]; [name], PhD; [name], MS

Table of Contents

| | |
|------------------------------------|----|
| A. Objectives | 2 |
| B. Background | 2 |
| C. Rationale | 4 |
| D. Experimental Approach | 6 |
| E. Statistical Analysis | 14 |
| F. Data Confidentiality Procedures | 15 |
| G. References | 16 |

This study proposal was submitted the National Institutes of Health and received a score of 12 (i.e. top 2 percentile). National Cancer Institute is considering it for funding.

A. Objectives

Primary Objective: Compare the intensity of dyspnea (numeric rating scale [NRS]) in the dexamethasone arm with that in the placebo arm at week 1.

Our working hypothesis is that dexamethasone will improve dyspnea compared with placebo in patients with cancer.

Secondary Objective #1: Compare the effects of dexamethasone with those of placebo in terms of personalized dyspnea response (based on a personalized dyspnea goal), unpleasantness of dyspnea, other symptoms, health-related quality of life, respiratory physiologic function, and adverse effects at week 1 and week 2, as well as the intensity of dyspnea at week 2.

Our working hypothesis is that short-term, high-dose dexamethasone will improve personalized dyspnea response, unpleasantness of dyspnea, symptom burden, health-related quality of life, and respiratory physiologic function, with limited adverse effects.

Secondary Objective #2: Identify predictive markers of dyspnea response to dexamethasone.

Our working hypothesis is that baseline inflammatory response (interleukin [IL]-1 β , IL-6, IL-8, IL-10, IL-6:IL-10 ratio, and tumor necrosis factor- α [TNF- α] levels) and certain patient characteristics (e.g., high baseline dyspnea and restrictive lung disease pattern) are associated with increased treatment response.

Secondary Objective #3: Determine the association between adverse event (AE) development (i.e. G3+ AEs, hospitalizations, specific adverse events) and the dose/duration of dexamethasone. *Our working hypothesis is that longer duration and higher dose is associated with greater AEs.*

Secondary Objective #4: Examine the similarities and differences between CTCAE and PRO-CTCAE reporting. *We will identify where CTCAE and PRO-CTCAE overlap and how they differ from each other.*

B. Background

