E.2.3. Secondary objective #2. The primary endpoint will be the baseline to day 7 difference in dyspnea NRS (>1.0 is considered clinically significant). We will use logistic regression analysis to identify independent predictors of this outcome, including baseline dyspnea NRS, restrictive or obstructive lung disease pattern, MIP, sex, and baseline inflammatory cytokine levels (IL-1 β , IL-6, IL-8, IL-10, and TNF- α). We will plot the data and use residual analyses to verify assumptions of the model and take appropriate actions if they appear to be validated (e.g., transforming the data). We will use the variance inflation factor to identify collinearity. With 116 dexamethasone-treated patients, we would have at least 80% power to detect an odds ratio of 2.5 (for a one-unit change in a normally distributed marker) if the response probability is at least 30% (assuming 5% alpha and a correlation between the marker and the other factors in the model of 0.30). As an exploratory analysis, we will perform a similar analysis to that described for the primary endpoint to determine whether patients achieved their personal goal in dyspnea improvement. We will perform a similar exploratory linear regression analysis using

the difference between the day 7 and baseline dyspnea NRS scores as the endpoint. Additional exploratory correlative analyses will be conducted for changes in inflammatory markers between day 7 and baseline.

E.2.4. Secondary objective #3. We will calculate summary statistics for duration of dexamethasone dosing and cumulative dexamethasone dose. Two-sample t-tests or Wilcoxon rank sums tests will be used to examine whether binary events, such as adverse events, are associated with higher doses or duration of dexamethasone. If number of hospital admissions follows a Poisson distribution or zero-inflated Poisson distribution, we will use the appropriate model to examine the association of number of hospitalizations with cumulative dose and duration. All patients, regardless whether they received placebo, will be used to examine dose and duration initially. In these analyses, dose and duration for patients who received placebo will be set to zero. In a second set of analyses, only those patients who received dexamethasone will be included in the analyses. All testing will be 2-sided with 5% alpha. We will consider limiting the false detection rate to 10%.

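### E.2.4's pooled dose and duration tests mainly restate the dexamethasone-versus-placebo contrast, and the plan does not say which analysis set answers secondary objective #3

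*Combined protocol and SAP*

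**What the plan says.** Section A gives the working hypothesis for secondary objective #3: "longer duration and higher dose is associated with greater AEs".

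Section E.2.4 sets out the analysis in two stages.

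- **First set.** "All patients, regardless whether they received placebo, will be used to examine dose and duration initially". For placebo patients, "In these analyses, dose and duration for patients who received placebo will be set to zero".
- **Second set.** "In a second set of analyses, only those patients who received dexamethasone will be included in the analyses".

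For binary events the method is: "Two-sample t-tests or Wilcoxon rank sums tests will be used to examine whether binary events, such as adverse events, are associated with higher doses"; treatment length is tested in the same way. For hospital admissions, if a Poisson or zero-inflated Poisson distribution fits, "we will use the appropriate model to examine the association of number of hospitalizations with cumulative dose and duration". No arm term appears in either method. On error control, "All testing will be 2-sided with 5% alpha", and a 10% false-discovery limit is only to be considered.

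E.2.4 does not name the set that answers the objective, does not say what is concluded if the two sets disagree, and gives no time window for events or exposure.

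**The concern.** A comparison of mean dose between patients with and without an event is informative about dose only if dose varies for reasons other than arm. Here it hardly does. Section D.5 gives every dexamethasone patient the same blinded-phase schedule, so within that arm exposure differs only through early stopping and missed doses. Adding placebo patients at exactly zero makes the step from none to some the dominant contrast.

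Suppose the drug raises event risk by the same amount in everyone who takes it. The first set would then tend to report that both higher dose and longer duration go with more adverse events. Those two findings would be close to one arm difference stated twice. A conclusion that less or shorter treatment is safer could then rest on data that say nothing about it.

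**Working it through.** **Inputs from the document.** Planned size is 134 dexamethasone and 67 placebo (D.1, E.1), so the dexamethasone fraction is π = 134/201 = 2/3. Blinded-phase exposure (D.5) is 16 mg/day × 7 + 8 mg/day × 7 = 112 + 56 = 168 mg over 14 days. Open-label exposure, offered to both arms (D.5), is 8 × 7 + 4 × 7 = 84 mg over a further 14 days. E.2.4 states no power or error rate, so there is no figure of the plan's to reproduce.

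**Assumptions.** Event and hospitalisation rates, and the stopping pattern: 15% of the dexamethasone arm (borrowing E.1's attrition figure) or 35%, stopping uniformly on days 1 to 13.

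**Step 1: share of exposure variance explained by arm.** With mean m and variance v of exposure in the dexamethasone arm and zero in the placebo arm,

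R² = π(1−π)m² / [π(1−π)m² + πv].

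- *Duration, 15% stopping.* m = 0.85×14 + 0.15×7 = 12.95. v = 0.85×196 + 0.15×63 − 12.95² = 8.35. R² = 37.27 / (37.27 + 5.57) = 0.87.
- *Dose, 15% stopping.* Early stoppers average (448 + 840)/13 = 99.08 mg, with mean square (35,840 + 118,720)/13 = 11,889. m = 0.85×168 + 0.15×99.08 = 157.66. v = 0.85×28,224 + 0.15×11,889 − m² ≈ 917. R² = 5,524 / (5,524 + 611) = 0.90.
- *35% stopping.* Simulated shares are 0.73 for duration and 0.79 for dose.
- *Open-label exposure counted, half of completers entering (assumed).* The share is about 64% for duration and 78% for dose.

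In the blinded phase dose and duration correlate at 0.995 or more, so the two tests are nearly one test. If everyone took the full schedule, v = 0 and the pooled test would be exactly the arm comparison.

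**Step 2: rejection rates.** Event risk is constant within each arm and unrelated to dose, duration or stopping. The table uses 134:67, 15% stopping and 1,500 trials per row; entries are the percentage with p < 0.05.

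| Events, placebo vs dexamethasone | Pooled t, dose | Pooled Wilcoxon, dose | Pooled t, duration | Dexamethasone-only, dose (t / Wilcoxon) | Plain arm test |
|---|---|---|---|---|---|
| 20% vs 20% | 4.5 | 4.9 | 4.5 | 3.7 / 3.9 | 5.0 |
| 10% vs 20% | 38.7 | 37.5 | 37.5 | 3.9 / 4.5 | 42.8 |
| 10% vs 30% | 89.9 | 87.5 | 88.7 | 3.5 / 4.4 | 92.8 |
| 20% vs 40% | 78.6 | 76.5 | 77.3 | 4.7 / 4.8 | 84.3 |

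Across 134:67 and 116:58, with 15% or 35% stopping, the pooled tests reject in 29–39%, 75–90% and 64–79% for the last three rows. The dexamethasone-only tests stay at 3.5–5.7%. In those three rows the pooled dose t-test and the arm test reach the same decision in 82–95% of trials.

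**Step 3: hospitalisations.** A pooled Poisson model of admissions on dose (means 0.3 vs 0.1, or 0.4 vs 0.2) rejects in 56–79%. Adding an arm term brings the dose coefficient to 2.8–5.2%, the same as the dexamethasone-only model.

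**Step 4: stopping caused by events.** Let 20% of dexamethasone patients with an event stop early because of it, still with no dose effect. The dexamethasone-only dose test then rejects in 40–48% of trials, because patients with events accumulate less drug. The pooled dose tests fall to 8–47%, against 45–84% for the plain arm test. The second set is therefore not a clean reference either, and the pooled tests are a poor version of the arm comparison.

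**The case against.** The strongest reply is that the plan already contains the better analysis. Any exposure versus none, followed by a look within the exposed, is a common sequence, and E.2.4 prespecifies both steps. Zero is a dose, and the objective does not restrict itself to treated patients, so a rejection driven by the step from zero is a real association under a coarse label. This stands. A reader might infer that the pooled tests have inflated type I error and reject when nothing is happening. The check does not support that: with 20% events in both arms and stopping unrelated to events they reject in 4.2–5.9%. Nor are they identical to the arm comparison unless adherence is complete.

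A second reply is that exposure may vary more than the blinded schedule implies. D.1.4 speaks of 2–4 weeks of treatment and D.1.6 of exploring use beyond 2 weeks. With the open-label schedule added, dexamethasone-arm exposure could reach 168 + 84 = 252 mg over 28 days. This stands in part. If half of completers enter, pooled duration rejections fall to 29% at 10% vs 20% and 62% at 20% vs 40%, still far above 5%. It also raises a further problem: placebo patients are offered open-label dexamethasone, and Table 3 records adverse effects at days 28 and 42, so zero is not their exposure once they take it.

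A third reply is that this is a secondary safety objective and that E.2.2 separately compares grade 3 or higher treatment-related toxicity by arm. That limits the consequence but does not settle what E.2.4 concludes. The statement that results are hypothesis-generating stands in E.2.2, not in E.2.4.

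**Conclusion.** The concern holds in a limited form. The first analysis in E.2.4 mainly measures dexamethasone versus placebo while being described as a test of dose and duration. When the drug raises risk equally at every exposure, it will often appear to support the working hypothesis. The sizes above depend on assumed event rates and stopping patterns; the mechanism depends only on the zero coding, the single schedule and the missing arm term.

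Two tempting conclusions go too far. The right question is not missing from the plan, since the dexamethasone-only set asks it; what is missing is a statement that this set answers objective #3. And moving to that set as it stands does not solve the problem, because dose among treated patients varies only through stopping and missed doses, which events can cause. The primary efficacy analysis and the sample size are unaffected.

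**What to change.** Amend E.2.4 as follows.

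1. Replace the pooled t and Wilcoxon tests with a direct comparison of events by arm, labelled any dexamethasone versus none in the blinded phase.
2. Base statements about dose and duration on the dexamethasone-only set already planned, or on a pooled model with an arm term plus dose (and, separately, duration). Say that this is the analysis that answers objective #3. Add the arm term to any pooled hospitalisation model.
3. Count only dose and days accrued before the event, with a comparable time at risk for patients without events, for example by entering exposure as a time-varying covariate.
4. State the event and exposure window. If it extends past day 14, record open-label exposure for placebo patients instead of zero, and say whether they then belong to the dexamethasone-only set.
5. Report dose and duration results as exploratory and non-randomised, and note that dose and duration can hardly be separated under one schedule.

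The cost is plan wording, an extra model term and somewhat more programming for the time-varying exposure. It needs dated events and dated dosing, so the sponsor should confirm that the daily contacts, pill counts and adverse event forms supply them. The dose and duration results will be significant less often, because they no longer borrow the arm difference.
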